8.3.5. Electronic Diary

All participants will be required to complete a reactogenicity e-diary after each vaccination given at Visits 1 and 201 through an application installed on a provisioned device or on the participant's own personal device. All participants will be asked to monitor and record local reactions, systemic events, and use of antipyretic medication for 7 days from the day of administration of the study intervention given at Visits 1 and 201. The reactogenicity e-diary allows recording of these assessments only within a fixed time window, thus providing the accurate representation of the participant's experience at that time. Data on local reactions and systemic events reported in the reactogenicity e-diary will be transferred electronically to a third-party vendor, where they will be available for review by investigators and the Pfizer clinicians at all times via an internet-based portal.

At intervals agreed to by the vendor and Pfizer, these data will be transferred electronically into Pfizer's database for analysis and reporting. These data do not need to be reported by the investigator in the CRF, unless the participant missed an e-diary entry and the participant experienced a prompted local reaction or systemic event, in which case any missed entries should be included in the AE CRF.

Investigators (or designee) will be required to review the reactogenicity e-diary data online at frequent intervals as part of the ongoing safety review.

The investigator or designee must obtain stop dates from the participant for any ongoing local reactions, systemic events, or use of antipyretic medication on the last day that the reactogenicity e-diary was completed. The stop dates should be documented in the source documents and the information entered in the CRF.

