9.3.1. General Considerations

CIs for all endpoints in the statistical analysis will be presented as 2-sided at the 95% level unless specified otherwise.

The safety analyses are based on the safety population. Participants will be summarized by vaccine group according to the study interventions they actually received. Completely missing reactogenicity e-diary data will not be imputed; missing AE dates will be handled according to the Pfizer safety rules. Missing e-diary data not recorded in the e-diary will be recorded on the AE CRF. Therefore, the primary analysis will use reactogenicity recorded as AEs in the CRF to impute the missing e-diary data.

For all the immunogenicity endpoints, the analysis will be based on the evaluable immunogenicity population. Antibody titers below the LLOQ or denoted as BLQ will be set to 0.5 × LLOQ for immunogenicity analysis. No other missing assay data will be imputed in the analyses. All immunogenicity analyses will be performed after the imputation of the antibody concentrations or antibody titers that are below the LLOQ.

An additional analysis may be performed based on the mITT immunogenicity population if there is a large enough difference in sample size between the mITT immunogenicity population and the evaluable immunogenicity population. Participants will be summarized according to the vaccine group to which they were randomized. Missing serology data will not be imputed.

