10.11.9.3.1. General Considerations for Substudy A

Refer to Section 9 for general considerations of statistical analyses.

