Presence of any local reaction.	The reaction is reported as "yes" with a diameter of >2.0 cm for redness/swelling or "yes" for pain any day from Day 1 through Day 7.	For all 3 local reactions, participant reports "no" (or "yes" with a diameter ≤2.0 cm for redness/swelling) on all 7 days (Day 1 through Day 7) or as a combination of "no" (or "yes" with a diameter ≤2.0 cm for redness/swelling) and missing on all 7 days. (Day 1 through Day 7).	Participant does not report any data for all 3 local reactions on all 7 days (Day 1 through Day 7).

a. The variables will be derived for any of the local reactions (redness, swelling, and pain at the injection site) and for any of the severe local reactions within the interval from Day 1 through Day 7 after vaccination.

Severity and Maximum Severity

Redness and swelling will be measured and recorded in measuring device units (range: 1 to 21) and then categorized during analysis as absent, mild, moderate, severe, or potentially life-threatening based on the grading scale in Table 5. Measuring device units can be converted to centimeters according to the following formula: 1 measuring device unit = 0.5 cm. Pain at the injection site will be assessed by the participant as absent, mild, moderate, or severe according to the grading scale in Table 5.

Mild Moderate Severe Potentially (Grade 1) Life-Threatening (Grade 2) (Grade 3) (Grade 4) Pain at the Does not interfere Prevents daily Emergency room Interferes with injection site with activity. activity. activity. visit or hospitalization for severe pain. Redness >2.0 cm to 5.0 cm >5.0 cm to 10.0 cm >10 cm Necrosis or (11 to 20 measuring exfoliative

device units).

device units).

>5.0 cm to 10.0 cm

(11 to 20 measuring

(≥21 measuring

(≥21 measuring

device units).

device units).

>10 cm

dermatitis.

Necrosis.

Table 5. Local Reaction Grading Scale

(5 to 10 measuring

>2.0 cm to 5.0 cm

(5 to 10 measuring

device units).

device units).

Swelling

For each local reaction, the maximum severity grade will be derived for the e-diary collection period (Day 1 through Day 7, where Day 1 is the day of each vaccination) as follows:

maximum severity grade = highest grade (maximum severity) within 7 days after vaccination (Day 1 through Day 7) among severity grades where the answers are neither "no" nor missing for at least 1 day during the interval from Day 1 through Day 7.

Duration of Each Local Reaction (First to Last Day Reported)

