The safety analyses are based on the safety population. Participants will be summarized by study intervention group according to the study interventions they actually received. Completely missing reactogenicity e-diary data will not be imputed; missing AE dates will be handled according to the Pfizer safety rules.

For all the immunogenicity endpoints, the analysis will be based on the evaluable immunogenicity population.

An additional analysis may be performed based on the mITT population if there is a large enough difference (>10%) in sample size between the mITT population and the evaluable immunogenicity population. Participants will be summarized according to the study intervention group to which they were randomized.

Vaccinated but not randomized: These participants will be included in the safety population for safety analysis and will be reported under the study intervention based on the vaccine received but will be excluded from immunogenicity analyses.

Randomized but not vaccinated: These participants will be included in the randomized population but will be excluded from safety analyses.

Randomized but received incorrect vaccine: These participants will be excluded from the evaluable population for immunogenicity but will be included in the mITT population for immunogenicity analyses if data are available and will be reported under the study intervention based on the randomized vaccine. These participants will also be included in the safety population for safety analysis and will be reported under the study intervention based on the vaccine received.

For participants enrolling at multiple sites: Any participants enrolling at more than 1 site in the study will be removed from all populations. These participants will be followed for safety and reported separately from the other participants.

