5.3.1.1. Reactogenicity Data

Completely missing reactogenicity e-diary data will not be imputed.

For derived variables based on reactogenicity data, if any day of the 7-day e-diary is available, the "any day (Day 1 through 7)" data will be considered nonmissing.

The reactogenicity data are collected through the reactogenicity e-diary, which does not allow participants to skip the question. Therefore, for a specific day, if the e-diary data are transferred for that day, all the reactogenicity data for the participant on that day are nonmissing. No missing reactogenicity data will be imputed other than what is described in Section 3.1.1 and Section 3.1.2.

In summary, for any participant with all 7 days of the e-diary missing, this will not be included in the analysis (ie, assuming MCAR). If only 1 to 6 days of e-diary data are transferred, the reactogenicity data for the missing day(s) are considered as answering "no" for all reactions. This is based on the common assumption that no reports mean no events.

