6. ANALYSES AND SUMMARIES

6.1. Primary Endpoints

6.1.1. Local Reactions and Systemic Events

6.1.1.1. Main Analysis

- Estimand strategy: Treatment policy (Section 2.2.1).
- Analysis set: Safety population (Section 4).
- Analysis methodology: 95% CI of the proportion of participants reporting each event, using the Clopper-Pearson method (Section 5.2.1).
- Intercurrent events and missing data: The participants without any e-diary data
 throughout the 7 days after vaccination will be excluded from the analysis at that
 vaccination; for participants who discontinue, all collected data will be included;
 intermediate missing values will not be imputed. Partially missing e-diary data are
 imputed as "no" (Section 5.3.1.1); e-diary data that are confirmed as errors will not be
 used for analysis.

- Analysis timing: Day 1 through Day 7 after vaccination.
- Reporting results:
 - O Descriptive statistics, including the proportion (%), the numerator (n) and the denominator (N) used in the proportion calculation, and the 95% CI for percentage using the Clopper-Pearson method, will be presented for each study intervention group and overall, for participants 18 through 64 years of age and ≥65 years of age separately and combined.
 - O Bar charts with the proportions of participants for each and any local reaction, and each and any systemic event, through the 7 days following vaccination will be plotted for each study intervention group and overall. The bars will be divided into severity categories to highlight the proportions of participants by maximum severity, for participants 18 through 64 years of age and ≥65 years of age separately and combined.

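### For partly completed e-diaries in Substudy A, the SAP codes missed days as 'no' while the current protocol fills them from AE CRF reactions, so the two documents define different primary reactogenicity analyses

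*SAP*

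**What the plan says.** **Protocol.** Section 9.3.1 states that e-diary data missing from the diary will be recorded on the AE CRF and that "the primary analysis will use reactogenicity recorded as AEs in the CRF to impute the missing e-diary data". The Substudy A statistical section does not set its own rule. Section 10.11.9.3.1 says only: "Refer to Section 9 for general considerations of statistical analyses". Section 8.3.5 covers vaccinations at Visit 1 (Substudy A) and Visit 201 (Substudy B). It deals with a participant who misses a diary entry and has a prompted reaction, "in which case any missed entries should be included in the AE CRF".

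**Substudy A SAP (version 2, 19 Jan 2023).** Section 5.3.1.1 says that if only 1 to 6 diary days are transferred, "the reactogenicity data for the missing day(s) are considered as answering 'no' for all reactions". It adds: "No missing reactogenicity data will be imputed other than what is described in Section 3.1.1 and Section 3.1.2". Section 6.1.1.1 repeats this for the main analysis: "intermediate missing values will not be imputed. Partially missing e-diary data are" set to 'no'. Table 3 codes any mix of 'no' and missing days as absence of the reaction. Section 4 carries over one protocol sentence, "Completely missing reactogenicity e-diary data will not be imputed; missing AE dates will be handled according to the Pfizer safety rules", but not the CRF sentence that accompanies it in the protocol. In Section 3.1.1, maximum severity is taken "among severity grades where the answers are neither" 'no' nor missing. The CRF enters the derivation only as a source of end dates for duration.

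**Substudy B SAP (version 2, 22 Feb 2024).** Section 5.3 fills partly missing diaries from the AE CRF first and counts only the remaining days as 'no'. Appendix 2 takes the highest grade across data sources.

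**The concern.** Local reactions and systemic events are primary endpoints of Substudy A. The SAP justifies its rule by assuming that the absence of a report means the absence of an event. That assumption fails where a report exists but sits on the AE CRF. The protocol expects such reports: Section 8.3.5 creates them, and the Substudy A stopping rules (Section 10.11.8.6) mention prompted reactions recorded either in the e-diary or as AEs.

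Three things are at stake. An analyst cannot satisfy both documents. One event could be absent from the reactogenicity table and present in the AE table. Substudies A and B would also count the same kind of case differently. No sensitivity analysis in Section 6.1.1.2 of the Substudy A SAP brings in CRF reactions, so the difference would not be visible.

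**Working it through.** **1. The two rules by diary status**

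| Diary days transferred | Protocol 9.3.1 | Substudy A SAP 5.3.1.1 and 6.1.1.1 |
|---|---|---|
| 7 | nothing to fill | nothing to fill |
| 1 to 6 | missed days filled from AE CRF reactions | missed days coded 'no' |
| 0 | not imputed | participant excluded |

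The rules differ only in the middle row.

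**2. Direction of the difference.** A participant with 1 to 6 days is in the denominator under both rules, because the SAP treats any-day data as nonmissing once one day is available. Only the numerator can differ.
- *Any-day presence* differs only if the AE CRF holds the reaction for a missed day and the participant reported it on no completed day.
- *Maximum severity* differs only if the worst grade fell on a missed day.
- In both cases the SAP value is equal to or lower than the protocol value. Onset day and duration may also change.

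**3. Group size.** Protocol Section 10.11.9.5 plans about 30 participants per vaccine group in each age stratum, so about 60 with the strata combined. As a check on n = 30, 1 − (1 − p)^30 gives 14.0%, 26.0%, 45.5%, 78.5% and 88.7% for p = 0.5%, 1%, 2%, 5% and 7%, which reproduces Protocol Table 7. The documents give no figure for the disputed rule itself.

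**4. Shift per affected participant.** 1/30 = 3.3 percentage points; 1/60 = 1.7 points.

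**5. Effect on a reported rate.** Exact Clopper-Pearson 95% intervals, the method both documents specify. The counts of 1 to 3 affected participants are an assumption for illustration.

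| Affected | Event reported as 0/30 under the SAP | Event reported as 15/30 under the SAP |
|---|---|---|
| 0 | 0% (0 to 11.6) | 50.0% (31.3 to 68.7) |
| 1 | 1/30 = 3.3% (0.1 to 17.2) | 16/30 = 53.3% (34.3 to 71.7) |
| 2 | 2/30 = 6.7% (0.8 to 22.1) | not computed |
| 3 | 3/30 = 10.0% (2.1 to 26.5) | 18/30 = 60.0% (40.6 to 77.3) |

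The rows for 1 to 3 show what the protocol rule would give.

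**6. The same effect as a rate.** Let p be the any-day rate under the protocol rule. Let m be the share of those participants whose only report is an AE CRF record for a missed day. The SAP then reports p(1 − m), which is lower by p × m. For an assumed m of 2% to 10%:
- p = 10%: 0.2 to 1.0 points lower
- p = 30%: 0.6 to 3.0 points lower
- p = 60%: 1.2 to 6.0 points lower

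**The case against.** **Version lag.** The Substudy A SAP matches Amendment 2 (9 Dec 2022). The amendment log lists the missed-entry text in Section 8.3.5, and an edit to Section 9.3.1, under Amendment 5 (15 Aug 2023). On that history the protocol moved and the SAP stayed behind. A reader might infer that the sponsor deliberately changed a primary analysis in the SAP without the amendment promised in SAP Section 2.1. The documents do not support that. Lag explains the mismatch, but it does not remove it: the current protocol and the current Substudy A SAP still disagree.

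**CRF capture.** The protocol rationale (Section 2.1) says the internal review committee reviewed Substudy A safety data in March and May 2023, before the logged site instruction. Many diaries were therefore finished before sites were told to enter missed reactions on the AE CRF. This stands: the CRF-based rates for Substudy A may be incomplete.

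**Grading and timing.** AE CRF events are graded on a general intensity scale, which is not the same as the diary scale. The SAP also requires redness or swelling above 2.0 cm. The sponsor was unblinded and had already seen data, so a change of derivation now is open to the charge of being post hoc. These points stand and bear on the choice of remedy.

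**Stronger readings that a reader might infer.**
- *Every missed day becomes 'no'.* Not so: participants with all 7 days missing are excluded.
- *Every CRF reaction drops out of the rates.* Not so: the any-day rate changes only if the reaction appears on no completed day, and the event can still appear in the AE summaries.
- *Confirmed Grade 4 reactions are lost.* This is inference. Section 3.1.1 lists a Grade 4 local reaction variable without naming its source, and under the protocol only an investigator or medically qualified person can assign Grade 4. The handling is unclear rather than shown to be wrong.

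**The estimand.** SAP Section 2.2.1 keeps data collected after missed diary entries. The variable there is the e-diary item, so this does not bring CRF reactions in.

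**Conclusion.** The conflict is real but minor. For diaries with 1 to 6 days transferred, the protocol and the Substudy A SAP specify different primary reactogenicity analyses. The SAP version can only give equal or lower any-day presence and maximum severity. The size is 3.3 points per affected participant in a group of 30, or 1.7 points in 60. One participant is enough to move an uncommon severe event from 0/30 to 1/30.

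The total effect cannot be estimated, because the documents give neither a missed-day rate nor a CRF-capture rate; the ranges above rest on assumed values. Substudy A is descriptive with no hypothesis test, so no formal conclusion changes. The dating of the CRF rule rests on the amendment log, which notes that Section 9.3.1 was edited without describing the edit. The conflict between the current texts does not depend on that dating.

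**What to change.** **Preferred.** Amend the Substudy A SAP as follows.
- In Sections 5.3.1.1 and 6.1.1.1 and Tables 3 and 4, fill missed days first from prompted reactions on the AE CRF with onset on Days 1 to 7, then code the remaining missed days 'no'.
- In Sections 3.1.1 and 3.1.2, use the highest grade across sources, and name the CRF as the source for Grade 4.
- Report the e-diary-only result as a sensitivity analysis, as the Substudy B SAP does.
- State two limitations: CRF capture of missed-day reactions may be incomplete in Substudy A, and AE CRF events carry the general intensity grade. Say also how CRF redness or swelling without a measured diameter is handled.

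**Alternative.** If the e-diary-only rule is to stay primary for Substudy A, declare it in SAP Section 2.1, exempt Substudy A in Protocol Section 9.3.1, and report the CRF-supplemented rates as a sensitivity analysis.

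**Cost.** Either route needs limited rewording and no new data collection; the alternative also needs a protocol change. Both require merging whatever AE CRF records exist, and the Substudy B derivations can serve as the template. Reporting both results also answers the post hoc objection, because the reader sees the rate under each rule.

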5.3.2. Immunogenicity Data

Any assay results above the LLOQ are considered accurate, and their quantitated values will be reported. Antibody titers below the LLOQ, denoted as BLQ, or below the LOD will be set to 0.5 × LLOQ for GMT analysis. No other missing assay data will be imputed in the analyses. All immunogenicity analyses will be performed after the imputation of the antibody concentrations or antibody titers that are below the LLOQ.

When calculating a fold rise, the assay results will be converted to $0.5 \times LLOQ$ if assay results are < LLOQ, except when the prevaccination assay result is < LLOQ while the postvaccination result is $\ge LLOQ$, in which case the prevaccination value will be set to LLOQ. If both the numerator and denominator are < LLOQ, then both will be converted in the same way.

Values for sera that are insufficient (QNS), indeterminate results or values recorded as "not done" will be set to "missing." Additionally, any time point with no blood draws will not be included in the analysis. No imputation will be done for these missing values, as MCAR is assumed for immunogenicity data.

LLOQ results for each assay used in this study will be included in serology data transfer once they are available.

6. ANALYSES AND SUMMARIES

6.1. Primary Endpoints

6.1.1. Local Reactions and Systemic Events

6.1.1.1. Main Analysis

- Estimand strategy: Treatment policy (Section 2.2.1).
- Analysis set: Safety population (Section 4).
- Analysis methodology: 95% CI of the proportion of participants reporting each event, using the Clopper-Pearson method (Section 5.2.1).
- Intercurrent events and missing data: The participants without any e-diary data
 throughout the 7 days after vaccination will be excluded from the analysis at that
 vaccination; for participants who discontinue, all collected data will be included;
 intermediate missing values will not be imputed. Partially missing e-diary data are
 imputed as "no" (Section 5.3.1.1); e-diary data that are confirmed as errors will not be
 used for analysis.

- Analysis timing: Day 1 through Day 7 after vaccination.
- Reporting results:
 - O Descriptive statistics, including the proportion (%), the numerator (n) and the denominator (N) used in the proportion calculation, and the 95% CI for percentage using the Clopper-Pearson method, will be presented for each study intervention group and overall, for participants 18 through 64 years of age and ≥65 years of age separately and combined.
 - O Bar charts with the proportions of participants for each and any local reaction, and each and any systemic event, through the 7 days following vaccination will be plotted for each study intervention group and overall. The bars will be divided into severity categories to highlight the proportions of participants by maximum severity, for participants 18 through 64 years of age and ≥65 years of age separately and combined.

6.1.1.2. Sensitivity/Supplementary Analyses

To support the assessment of reactogenicity, the endpoints below, as specified in Section 3.1.1 and Section 3.1.2, will be summarized with the same analysis time point and analysis population:

- Duration (days) of each local reaction and each systemic event after vaccination.
- Onset day of each local reaction and each systemic event after vaccination.
- Presence of each and any severe local reaction and each and any severe systemic event, on each of the 7 days and for "any day (Day 1 through Day 7)."

The presentation of the results will include a basic descriptive summary without 95% CIs (Section 5.2.1).

These continuous endpoints will be summarized by displaying the n, mean, median, standard deviation, minimum, and maximum for each study intervention group and overall, for participants 18 through 64 years of age and ≥65 years of age separately and combined.

In addition, the proportions of participants reporting prompted local reactions and systemic events, by maximum severity level, with any e-diary errors will be included as a supplemental summary for participants 18 through 64 years of age and ≥65 years of age separately and combined.

